5.5 Study Visits, Data Collection, and Risk Management

Visits and length of participation

This study will take place in two parts and will have two consent forms, one for each part of the study. Participants may be asked to be involved in both parts of the study; recruitment efforts will take place separately.

Part 1: Using the TAP, a motor-driven computer controlled prosthesis, to inform development of the PFF.

During this part of the study, we will use the TAP to evaluate several different paired turning and flexing motion ratio settings. Based on the results we will select an optimal paired ratio setting(s) that will be used in the design of the PFF.

Visits and length of participation

Consent and data collection procedures will be done at the VA Puget Sound in Seattle. Participants will be asked to do two visits that may last up to 4 hours each. If we find that data are missing or corrupt participants may be asked to do another study visit. All procedures are for research purposes and provide no clinical treatment. Participants will be provided rest breaks throughout the procedures, and may request one at any time. We may call and/or email participants to remind them about upcoming study visits.

Visit 1

Eligibility

Participants' residual limb, prosthesis, and fitment will be examined to determine if they can participate in the study. The research prosthetist may adjust their prosthesis to optimize fitment. If a participant is unable to continue in the study they will be compensated for their effort.

Demographic Information

We will ask participants to provide us with the following required demographic information:

- Sex
- Race
- Ethnicity
- Veteran status

We will ask participants to provide us with the following study demographic information:

- Age
- Years since amputation
- Level and side of amputation
- Cause of amputation
- Body weight
- Height
- Prosthesis information (socket, liner, suspension, and foot type, category, and/or size

Self-Selected Walking Speed (SSWS) Tests

Participants will use their own prosthesis during these tests. Participants will be asked to walk several times, at their self-selected pace, for about 65-feet back and forth in a straight hallway. Participants will also be asked to walk at their own pace several times around a ~3-

foot radius circle. These tests will be used to determine each participants' straight line and circle SSWS.

Motion and Force Measurement

Participants will be asked to change into a tight-fitting shirt and shorts that we provide. A private area for participants to change clothes will be provided. We will record a series of standard body measurements such as height, weight, and leg length. We will attach up to 70 small reflective markers with double sided tape to specific locations on the participants' hands, trunk, legs, and feet.

During the walking tests in the lab, the infrared cameras will record the location and movement of the markers; they do not record a picture of the body. Data will also be collected by force plates embedded in the floor of the lab; participants will walk across and stand on the plates during the tests.

Tensionally Adaptive Prosthesis (TAP)

The research prosthetist will fit the TAP to the participants' socket. The TAP is a motorized, programmable prosthesis, it will be connected to a computer and power source with long wires. The wires will be routed so they are not a trip hazard. The TAP will be programmed with 5 different paired turning and flexing motion ratio settings. The different settings will change how the prosthesis feels (more or less compliant) during walking. Participants will practice walking on each of the settings until they feel confident/stable. If confidence and stability cannot be achieved the participant may not be able to continue in study.

The TAP's 5 paired motion settings will be tested in a randomized order. The first setting will be selected then participants will be asked to walk back and forth in a straight line several (approximately 3-6) times at their SSWS. Once we have enough data, participants will be asked to rate their satisfaction with the setting on a 0-10 scale. The same process will be repeated for each of the remaining settings.

After all five settings have been tested the research prosthetist will re-fit the participants' as-prescribed prosthesis. We will schedule the next study visit before participants leave or we will call them later to schedule it.

Visit 2

The procedures listed under "Motion and Force Measurement" will be used again during this visit. The research prosthetist will fit the TAP to participants' socket and they will be allowed to practice walking with it until they feel confident/stable.

The TAP's five settings will be tested in a randomized order. The first setting will be selected then participants will be asked to walk around a ~3-foot radius circle several (3-6) times at their SSWS. Participants will be asked to do the circle walking tests in both clockwise and counter-clockwise directions (randomized order). Once we have enough data, participants will be asked to rate their satisfaction with the setting on a 0-10 scale. The same process will be repeated for each of the remaining settings.

After all five settings have been tested the research prosthetist will re-fit the participants' as-prescribed prosthesis. We will schedule the next study visit before participants leave or we will call them later to schedule it.

Part 2: Build and evaluate the PFF

Informed by the results of Part 1, we will design, build and thoroughly bench test our PFF. We will build the PFF in a few sizes, and in left and right foot configurations to accommodate for participant variability. When ready, we will test the PFF with participants as described below.

Visits and length of participation

Consent and data collection procedures will be done at the VA Puget Sound in Seattle and participants will wear study assigned prostheses at home/in the community. Participants will be asked to do three visits that may last up to 4 hours each. If we find that data are missing or corrupt participants may be asked to do another study visit. All procedures are for research purposes and provide no clinical treatment. Participants will be provided rest breaks throughout the procedures, and may request one at any time. We may call and/or email participants to remind them about upcoming study visits.

Visit 1

Eligibility

Participants' residual limb, prosthesis, and fitment will be examined to determine if they can participate in the study. The research prosthetist may adjust their prosthesis to optimize fitment. If a participant is unable to continue in the study they will be compensated for their effort.

Demographic Information *If a participant completed Part 1 of the study then we will not collect this information again.*

We will ask participants to provide us with the following required demographic information:

- Sex
- Race
- Ethnicity
- Veteran status

We will ask participants to provide us with the following study demographic information:

- Age
- Years since amputation
- Level and side of amputation
- Cause of amputation
- Body weight
- Height
- Prosthesis information (socket, liner, suspension, and foot type, category, and/or size

Self-Selected Walking Speed (SSWS) Tests

Participants will use their own prosthesis during these tests. Participants will be asked to walk several times, at their self-selected pace, for about 65-feet back and forth in a straight hallway. Participants will also be asked to walk at their own pace several times around a ~3-foot radius circle. These tests will be used to determine each participants' straight line and circle SSWS.

Randomization to Study Prosthesis – At Home Acclimation

Participants will be randomized to wear the PFF or the standard-of-care prosthetic foot for the next 2 weeks at home/in the community during their normal daily activities. The research prosthetist will fit the PFF or standard-of-care foot to the participants as-prescribed socket and suspension system. Participants will be blinded to prosthetic foot type. The prosthetic feet will be covered with a sock and cosmesis and participants will be instructed not to remove the coverings from the foot. Participants will practice walking on the assigned foot until they feel confident/stable. If confidence and stability cannot be achieved the participant may not be able to continue in study. Participants will be instructed to contact us if they have any problems or concerns with the study prosthesis during the 2-week acclimation period. We will arrange to make prosthetic adjustments if needed. We will store the participants' prescribed prosthetic foot during the at-home acclimation periods.

Visit 2

After wearing the study prosthesis for approximately 2-weeks participants will return to the lab to do a series of walking tests.

Motion and Force Measurement

Participants will be asked to change into a tight-fitting shirt and shorts that we provide. A private changing area will be provided. We will record a series of standard body measurements such as height, weight, and leg length. We will attach up to 70 small reflective markers with double sided tape to specific locations on the participants' hands, trunk, legs, and feet.

During the walking tests in the lab, the infrared cameras will record the location and movement of the markers; they do not record a picture of the body. Data will also be collected by force plates embedded in the floor of the lab; participants will walk across and stand on the plates during the tests.

SSWS Walking Tests

While using the study prosthesis, participants will be asked to walk back and forth in a straight line several (approximately 3-6) times at their SSWS. Participants will also be asked to walk around a ~3-foot radius circle several (3-6) times at their SSWS. They will be asked to do the circle walking tests in both clockwise and counter-clockwise directions (randomized order).

Study Prosthesis – At Home Acclimation

The research prosthetist will fit participants with the other study prosthesis. Participants will remain blinded to the foot type. Participants will practice walking on the assigned foot until they feel confident/stable. If confidence and stability cannot be achieved the participant may not be able to continue in study. Participants will be instructed to contact us if they have any problems or concerns with the study prosthesis during the 2-week acclimation period. We will arrange to make prosthetic adjustments if needed.

Visit 3

After wearing the study prosthesis for approximately 2-weeks participants will again return to the lab to do a series of walking tests. The Motion and Force Measurement, and SSWS Walking Tests described in Visit 2 will be repeated. The research prosthetist will re-fit participants with their as-prescribed prosthetic foot.

Applicable to Parts 1 & 2

During study sessions, visitors and observers will not be allowed in the lab unless the participant agrees to their presence; the participant can change her/his mind at any time.

Photos and video

We may take video and photos of participants during portions of this study for documentation and use in research publications. To protect the identity and privacy of our participants, all videos and photos will be edited later to de-identify the images (e.g., bluring of faces, tattoos, and other distinguishing marks). No sound will be recorded to prevent voice identification.

Repository

Participants will be asked if they are interested in allowing their study data to be added to our de-identified data repository so that it may be used for additional research in the future. Participants who are interested will be asked to sign a separate consent form for the repository (MIRB# 00493). Once the consent form is signed, a copy of the data will be added to the repository on an ongoing basis throughout the course of the study.

Payment to Participants

Participants will receive \$50/hour for the first hour of each visit and then \$30/hour for each remaining hour of each visit to the VA Puget Sound (for both parts of the study). Participants involved in Part 2 of the study will be paid \$100 for each 2-week at-home acclimation period. For subjects traveling 20+ miles one way for appointments (40+ miles total), we will provide compensated mileage rates in accordance with the Veterans Affairs Beneficiary Travel program. This amount may fluctuate. To ensure accuracy, study staff will check to make sure the most up-to-date amount is being used prior to adding travel compensation to total compensation amount. Current mileage rates can be found at https://www.va.gov/HEALTHBENEFITS/vtp/beneficiary_travel.asp. For subjects traveling via ferry for appointments, we will provide full ferry fare compensation. We will not offer

compensation for other individuals traveling to the appointment with the participant. To ensure the most up-to-date fares are used, study staff will check the Washington State Department of Transportation ferry fare website (<https://www.wsdot.wa.gov/ferries/fares/>) prior to adding ferry fare compensation to total compensation amount. We will determine if travel compensation is required based on contact information recorded during enrollment. Checks will be mailed by the fiscal department about 6-8 weeks after each study visit or can be picked up at the VA Puget Sound within the same time frame. Participants that are screened out after consent will be compensated on a prorated basis as well as for any applicable travel compensation.

Risks and Risk Management

Risks associated with use of study provided prostheses and walking procedures

Please note, the increase in physical risks associated with participation in this study only represent a small increase from those encountered in daily life of the participant population.

It is possible that participants may experience an injury (e.g., arising from a trip or a fall while in the lab or while wearing a study provided prosthesis during the at-home acclimation periods) and/or discomfort (e.g., mild to moderate muscle soreness or other soft tissue irritation while in the lab or during the at-home acclimation period), because of walking with the study-provided prostheses. It is possible that a component failure or malfunction of the prostheses could cause a soft tissue injury (e.g., soreness, bruising, scrape) or other minor mechanical injury (e.g., knee or ankle joint soreness). Participants may feel fatigued during or shortly after the study visits. It is possible that participants may experience some emotional or physical stress while adapting to wearing an unfamiliar prosthesis. The motion analysis laboratory floor is clear of obstacles, level, dry, and rigid. Thus, walking in the lab is akin to walking on a well-maintained indoor floor. Participants will be instructed to inform us if they feel pain or discomfort during the procedures and we will stop the activities to address any reported issues as needed. Care will be taken to properly fit the prostheses. Participants will only be asked to walk at speeds they are comfortable with. To minimize the risk of TAP or PFF prosthesis failure, these devices will be thoroughly tested on a benchtop and a certified prosthetist will also evaluate the quality of the prostheses prior to them being worn by participants. The standard-of-care prosthetic foot is a commonly used, commercially available foot. Participants will be instructed to exhibit caution while acclimating to walking with a new or modified prosthesis. This is the same instruction provided when a patient receives a new or different prosthesis as part of a clinical prescription. Since participants will have a chance to wear each of the study assigned feet for about an hour in the laboratory setting, we do not expect any problems to arise during the two-week at home portion of the study. The study feet will be fit to the participants' current socket which will also help minimize the risk of skin irritation. Participants will be asked to contact us in the event of any study-related pain or injuries to schedule an examination.

In part 2 of the study, we may discover that participants have peripheral neuropathy with impaired sensation in their residual limb, or that the level of neuropathy or impaired sensation is different than participants were aware of. This may cause some level of stress. For dysvascular individuals, it is not uncommon for the residual lower-limb to have some level of

peripheral neuropathy with impairment of sensation. Semmes-Weinstein monofilament testing is a simple and non-invasive test normally administered to dysvascular patients to assess protective sensation on the level of the skin of the lower extremities. The selected monofilament test score threshold should minimize the risk of dysvascular participants being unable to notice skin irritation on their residual limb. If participants become distressed during the Semmes-Weinstein monofilament testing we will advise them to see their regular care provider.

The tape used to apply the markers may cause mild skin discomfort or irritation while worn or when removed (feels similar to removing a band-aid). Only trained study staff will place and remove the reflective markers. Participants may feel embarrassed while wearing the tight fitting clothing.

It is also possible that participants may experience stress or inconvenience by coming to the VA for multiple visits. Participants can stop their participation at any time.

The PI will ensure the study procedures are being properly followed by keeping the research staff well informed of the current study procedures through regular/ongoing contact. Although an injurious fall or a prosthetic component failure related to this protocol is unlikely, we will tabulate a list of any such reports that occur during the study and compare it with corresponding data available in the literature. This will allow us to analyze how much of an increased risk was due to the administered protocol. After each report of an AE, SAE or an unanticipated problem, we will evaluate study procedures for previously-assessed risks, and will determine whether any changes to the protocol are necessary to minimize risks. The study will be suspended until these changes have been fully implemented and approved by the IRB.

Privacy and Confidentiality

See section 7.0 below for Information Security, Privacy, and Confidentiality related procedures.

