- 1) Participants with a unilateral transtibial (below-knee) amputation (up to 40) will be fit with our motor-driven and computer controlled **torsionally adaptive prosthesis (TAP)**. The TAP can pair turning and flexing motion at different proportional settings; several paired motion ratio settings of turning (transverse plane motion) to flexing (sagittal plane motion) will be tested. Over two visits, participants will do a series of walking tests over level ground with the TAP set at different pairing settings (blinded and random order) while biomechanical data is collected. Satisfaction data will be collected for each setting. The results will be used to inform the design of the PFF.

Based on results from the TAP testing, we will design and build PFFs of various sizes and stiffnesses to compare to a standard-of-care prosthesis. In a blinded crossover experiment, over 3 visits, participants (up to 40) will be fit with the study prostheses (PFF or a standard-of-care prosthetic foot) in random order and wear each study prosthesis at home for 2 weeks. Participants will visit the laboratory to do a series of walking tests after each 2-week acclimation period.

List of Abbreviations

AE – adverse event

CPRS - Computerized Patient Record System

CRQ – Continuing Review Questionnaire

HIPAA – Health Insurance Portability and Accountability Act

ISO - Information Security Officer

IRB – institutional review board

PFF – Pivot-Flex Foot

PHI – protected health information

PI – Principal Investigator

PO – Privacy Officer

ROP – report of other problem

SA – specific aim

SAE – serious adverse event

SD – standard deviation

TAP – torsionally adaptive prosthesis

TT – transtibial

UW – University of Washington

VA – Veterans Affairs

Contents

Protocol Title: Pivot-Flex Foot

1.0	Key Study Personnel.....	5
2.0	Introduction.....	5
3.0	Specific Aims and Hypotheses.....	6
4.0	Resources and Personnel.....	6
5.0	Study Procedures.....	6
5.1	Study Design.....	7
5.2	Recruitment Methods and Initial Screening.....	7
5.3	Informed Consent Procedures.....	10
5.4	Inclusion/Exclusion Criteria.....	11
5.5	Study Visits, Data Collection, and Risk Management.....	11
5.6	Data Analysis.....	18
5.7	Withdrawal of Subjects.....	21
6.0	Reporting.....	21
7.0	Information Security, Privacy, and Confidentiality.....	211
8.0	Communication Plan.....	22
9.0	References.....	23

Protocol Title: Pivot-Flex Foot

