Satisfaction data from the experiment will be tabulated for straight and both directions of the circle walking trials at the five different coupling ratios (0, 1:6, 1:4, 1:3, and 1:2). This data will be processed and aggregated using project specific software (Matlab; Mathworks, Natick, MA).

We hypothesize that:

H2.1: When walking in a straight line, there exists a coupling ratio that maximizes satisfaction.

H2.2: When circle walking with the prosthetic limb on the inside of the turn, there exists a coupling ratio that maximizes satisfaction.

H2.3: When circle walking with the prosthetic limb on the outside of the turn, there exists a coupling ratio that maximizes satisfaction.

The statistical analysis to test these hypotheses (H2.1, H2.2, and H2.3) will require three Friedman analyses of variance (ANOVA). These analyses will test for differences between the five coupling ratios across the three different ambulatory activities. The experiment-wise significance will be set a priori at an alpha level of $p<0.05$ and a Bonferroni adjustment will be applied for multiple comparisons. All analyses will be performed using existing VA enterprise software (SPSS Statistics v22; IBM, Inc.). Exact p-values will be reported for each test.

The results of testing hypothesis 1 will be used to define the optimal coupling ratio. The coupling ratios (0, 1:6, 1:4, 1:3, and 1:2) will be placed in rank order and an evenly weighted rank average will be used to identify the coupling ratio that minimizes the transverse-plane moment. If this algorithm cannot distinguish between two or more coupling ratios, then a similar method will be used to rank the results from hypothesis 2. If neither algorithm can distinguish the optimal coupling ratio, then the investigative team will engage the clinical

team and use their experience to select a coupling ratio for use in specific aim 2. Please see our discussion of this issue in the potential problems section.

Specific Aim 2: Kinematic and kinetic data from the experiment will be analyzed to identify the peak transverse-plane moment and hip work while walking straight and in both directions of the circle walking trials while wearing the study prostheses. This data will be processed (Visual3D; C-Motion, Germantown, MD) and aggregated using project specific software (Matlab; Mathworks, Natick, MA).

We hypothesize that:

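### Part 1, Visit 2 describes one satisfaction rating per setting after both circle directions, but section 5.6 plans separate inside and outside satisfaction analyses (H2.2, H2.3)

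*Protocol*

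**What the plan says.** **Collection (protocol section 5.5, Part 1, Visit 2).** The steps come in a fixed order. "The TAP's five settings will be tested in a randomized order". At each setting the participant walks the circle: "Participants will be asked to do the circle walking tests in both clockwise and counter-clockwise directions (randomized order". Next, "Once we have enough data, participants will be asked to rate their satisfaction with the setting on a 0-10 scale". Then the loop: "The same process will be repeated for each of the remaining settings". Visit 1 uses the same rating sentence for straight-line walking. The Abstract describes collection in the same unit: "Satisfaction data will be collected for each setting".

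**Analysis (protocol section 5.6, Specific Aim 1).** "Satisfaction data from the experiment will be tabulated for straight and both directions of the circle walking trials", at five coupling ratios. H2.1 concerns straight walking. The circle is then split in two: "H2.2: When circle walking with the prosthetic limb on the inside of the turn, there exists a coupling ratio that maximizes satisfaction", and "H2.3: When circle walking with the prosthetic limb on the outside of the turn, there exists a coupling ratio that maximizes satisfaction". One Friedman test is planned for each of the three activities. The same section uses satisfaction as a tie-break: if the ranks of the transverse-plane moment cannot separate the ratios, the satisfaction results are ranked by a similar method. If that also fails, the clinical team is consulted.

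**SAP.** Satisfaction was not statistically analysed. The reasons given are the small sample and the variance expected in such data.

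**The concern.** The visit text and the analysis text use different units. At Visit 2 the thing rated is the setting, and the procedure repeats over settings, not over directions. The analysis needs a score for each setting in each direction.

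A single score given after both directions mixes walking with the prosthesis inside the turn and walking with it outside. A ratio that participants like in one direction and dislike in the other would appear only as a middling score, and the two parts cannot be recovered afterwards. The protocol treats direction as worth separating: it splits inside from outside in H1, H2, H3 and H4.

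Three things are at stake: the planned tests of H2.2 and H2.3, any satisfaction summary by direction, and the satisfaction tie-break that could help choose the ratio built into the Pivot-Flex Foot.

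**Working it through.** The plan gives no sample size, power or alpha figure specific to H2.2 or H2.3, so there is none to reproduce. The check is a count of ratings, followed by the consequences of the shortfall.

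**Inputs.** Five settings (section 5.5, and the five ratios in section 5.6). Three activities in the satisfaction analysis: straight, prosthesis inside, prosthesis outside (section 5.6). One rating per setting at Visit 1 and one per setting at Visit 2 (section 5.5, as written).

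**Ratings per participant.**

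| Activity | Needed (5.6) | Described (5.5) |
|---|---|---|
| Straight | 5 | 5 |
| Circle, prosthesis inside | 5 | 5 shared by both directions |
| Circle, prosthesis outside | 5 | (same 5) |
| Total | 5 x 3 = 15 | 5 + 5 = 10 |

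The shortfall is 15 - 10 = 5, all of it in circle walking. H2.1 is complete.

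**If the shared rating were entered under both hypotheses (an assumption; no document says this).** The Friedman statistic depends only on the ranks of the five scores within each participant. The same scores give the same ranks, so the two tests would be one test. On an arbitrary example of 15 participants by 5 settings, both gave chi-square 6.90 on 5 - 1 = 4 degrees of freedom, p = 0.14. In an evenly weighted tie-break over three lists, the circle rating would fill 2 of 3 places, a weight of 2/3. With two lists, straight and circle carry 1/2 each.

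**How much a blended score could hide (illustration; all inputs assumed).** The assumptions were 15 participants, a 2-point linear trend across the five settings that rises in one direction and falls in the other, between-participant SD 1.5, residual SD 1.5, scores rounded to the 0-10 scale, and an overall rating equal to the mean of the two directions. Over 2,000 simulated trials tested at 0.05, the direction-specific ratings gave a significant Friedman test in about 82% of runs each, and the overall rating in about 5%. This is an adverse case, chosen so that the trends cancel on averaging. Trends that run the same way in both directions would not cancel.

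**The case against.** **The visit text may only be incomplete.** It does not say that there is a single rating, and section 5.6 expects ratings for both circle directions. The intention may have been to ask after each direction, and the rating form is not among the documents. This stands as a limit: a reader might infer that direction-specific ratings were certainly never taken and that H2.2 and H2.3 can never be answered, and the documents do not establish that. They establish that the written procedure does not describe the ratings the analysis needs. Staff following it would take one per setting.

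**The SAP dropped the tests.** A reader might infer that a reported satisfaction result is wrong. The documents do not support this, because the SAP says satisfaction was not statistically analysed. However, its reasons are sample size and variance, not missing ratings, and it does not withdraw the tie-break, which works on ranks and needs no significance test.

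**Identical p-values and a 2/3 weight are hypothetical.** This is correct. Both require the circle rating to be used twice. Section 5.6 says only that a similar method will be applied, and two lists would fit that equally well.

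**The tie-break is remote, and the main hypotheses are untouched.** This is also correct. Satisfaction counts only if the moment ranks cannot separate the ratios. H1.2 and H1.3 use moments identified for each direction. The general H2 in section 3.0 asks only whether a preferred ratio exists within the range, which straight and circle ratings can address.

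**Conclusion.** The point holds as a mismatch between the collection procedure and the analysis it is meant to feed. As written, each participant gives 10 ratings where 15 are needed, H2.2 and H2.3 have no separate data, and the tie-break, if reached, has two distinct satisfaction lists (straight and circle).

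The effect is confined to the protocol's planned satisfaction tests, any summary of satisfaction by direction, and that conditional tie-break. No test reported under the SAP depends on it. H2.1 and the moment hypotheses are unaffected. Severity is moderate.

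The count rests on the plain reading of Visit 2, in which one rating follows both directions at each setting. If ratings were in fact taken after each direction, the fault reduces to an omission in section 5.5, and the two sections still need to be brought into line.

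**What to change.** In section 5.5, Part 1, Visit 2, state that the 0-10 rating is taken after the clockwise trials and again after the counter-clockwise trials at each setting. Code each rating as prosthesis inside or outside from the side of amputation, which is already recorded with the demographic information. The Visit 2 count becomes 5 x 2 = 10 and the total 5 + 10 = 15, as section 5.6 requires. The cost is five extra questions per participant in a visit of up to 4 hours, with no extra walking.

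The SAP is dated 23Sep2025 and written in the past tense, so the Part 1 data may already be in. In that case, first state what was recorded:

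- If there was a rating after each direction, correct section 5.5 to say so.
- If there was only one circle rating per setting, merge H2.2 and H2.3 into a single circle-walking hypothesis, report satisfaction for straight and circle only, and use two lists in the tie-break. This costs a text change and the loss of any direction-specific statement about satisfaction.
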